## Research Question and Aims

**Hypothesis:** Patients with Obstructive Sleep Apnea (OSA) and obesity will have positive behavior changes as the result of participating in a remote monitoring and health coaching program. The positive behavior changes include improved control of their OSA via adherence to prescribed medical devices, reductions in obesity and improved quality of life.

**Aims, purpose, or objectives:** Mayo Clinic in collaboration with Minnesota Health Solutions (MHS) will develop a data driven system for persons with severe obesity sleep apnea that utilizes remote monitoring with health coaching to create behavior changes aimed at improving health and quality of life. In previous NIH funding, Mayo and MHS have previously developed a home-based monitoring system with health coaching for COPD patients (IRB's 14-009016, 17-009449, 18-002453). MHS will modify the system for patients with severe obesity sleep apnea. Mayo Clinic will conduct the at-home feasibility testing and qualitative interviews.

**Background:** Obstructive sleep apnea (OSA) is a disorder characterized by episodic cessation of breathing during sleep with intermittent hypoxemia and sleep fragmentation. Its effects go far beyond sleep and it is associated with decreased neurocognitive function, reduced quality of life and increases in hypertension, insulin resistance and cardiovascular disease. The prevalence of clinically significant OSA has been estimated at 7% for adult males and 5% for adult females. Researchers have found though that OSA likely has a higher undiagnosed prevalence, up to 21% in the general population, and that prevalence increases with age. The strongest risk factor for developing OSA is obesity and it is estimated that more than half of the prevalence of OSA is attributable to excess body weight.

First line therapy for OSA has been positive airway pressure (PAP); however, despite many technological advances in PAP therapy, adherence to use, a behavior, remains a problem. Using best current practices, acceptable PAP adherence at 31-90 days is seen in only 75% of patients and only 65% will be adherent at one-year. Although PAP is considered the best single therapy for OSA, this is only applied during sleep and only addresses airway patency with no direct impact on obesity or the many comorbidities that contribute to and perpetuate OSA. Most of the chronic conditions associated with sleep apnea are related to behavior. Hence, there is a need for interventions that promote compliance with PAP and promote behavior change to improve obesity and other comorbidities. We propose to develop a remote system that utilizes effective digital intervention techniques in combination with data monitoring and health coaching to create behavior change. Health coaching informed by biomonitoring can create the conditions for behavioral change by providing motivation and feedback, which support the development of self-efficacy to create change.

Health coaching has been shown to improve outcomes in the most prevalent chronic conditions including COPD, diabetes and heart failure. Health coaching via telehealth provides a unique engagement that supports behavior change through the theory of planned behavior. Through coaching, patients have the opportunity to develop the motivation to change. Remote monitoring provides patients and the health coach direct feedback that can bring awareness of measures, such as activity level, weight, sleep quality and PAP adherence. Properly presented and used these data become a unique tool to inform the dialogue for behavior change. Patients are able to develop the self-efficacy to support behavior change. Best practices in digital intervention are well-suited to health coaching and support the development of a system that is scalable, accessible, and billable.

Multiple studies have shown that the annual health care costs of OSA patients are double the costs for age and sex matched controls. These additional costs are due to hospitalizations, physician fees, specialist fees, and prescriptions. Additionally, researchers have shown that effectively treated patients show a gradual decrease in healthcare costs while matched controls continue to show an increase in healthcare costs.

Obesity is also associated with increased health expenditures compared to people with a normal body weight and it is estimated that 9% of annual health expenditures are due to obesity. Most of this extra cost is due to health care conditions associated with obesity, including diabetes and cardiovascular disease. However, it is difficult to separate the contributions of OSA and obesity from the costs of treating common comorbidities.

There are multiple bi-directional relationships between a wide range of comorbidities and OSA and there is substantial sharing of genetic polymorphisms between OSA and obesity. OSA influences hormonal regulation of appetite and metabolism via intermediaries such as leptin and ghrelin, and treatment with PAP tends to influence these factors in favor of weight loss. However, without changes in activity and diet, most studies demonstrate ongoing weight gain in newly treated obese OSA patients. Both obesity and OSA have independent contributions to cardiovascular risk. While PAP therapy remains an essential part of OSA treatment, its use does not directly impact obesity or all of the comorbidities associated with severe OSA syndrome. Most of the chronic conditions associated with OSA are related to behavior. Additionally, PAP has significant problems with adherence, a behavior.

There is a need for interventions that lead to behavior change, resulting in weight loss and reduced risk of cardiovascular events, and these should be recommended to all patients with OSA. A consistent finding in clinical studies is that weight reductions result in improvement in OSA symptoms. In a group of patients with obesity, diabetes and OSA, an intensive lifestyle intervention led to more weight loss and more than three times the rate of remission from OSA than the controls receiving standard diabetes support and education.

Health coaching has demonstrated effectiveness for behavior change and chronic disease management. While still limited, there is growing evidence that health coaching can be used for weight management, physical activity promotion, and medication adherence. A recently completed meta-analysis that included 15 randomized trials found that health coaching could easily be delivered and provided motivation strategies for behavior change (physical activity, dietary behavior, health responsibility and stress management) among patients with cardiovascular risk factors. A previous study by PI [name] that utilized health coaching for patients with severe COPD after hospitalization showed decreased readmission and sustainable improvements in quality of life. In another study by [name] of severe obesity in patients with chronic lung disease, an eight week intervention with weekly health coaching calls resulted in weight loss and improvements in body composition, walking tests, mindful eating behavior and quality of life. Additionally, this study incorporated the Weight Watchers app for recording food and an activity monitor to capture daily steps.

The use of remote monitoring devices offers an additional opportunity to enhance health coaching. A pilot study that combined wearable devices with health coaching to promote healthy lifestyle changes in overweight patients resulted in clinically significant weight loss over 16 weeks. Participants had good adherence to wearing their devices and lost more weight as time went along. The researchers hypothesize that effectiveness was increased by participants completing questions in advance of health coaching sessions, which allowed the focus in sessions to be on relationship building and problem solving. In another recently completed study that used health coaching and remote monitoring for weight loss in obese patients, participants who received health coaching had increased compliance with device adherence and higher rates of weight loss than participants who did not receive the health coaching. Health coaching combined with remote monitoring offers the possibility of a relatively inexpensive intervention that is scalable, billable and able to be delivered remotely. Patients who have difficulty accessing a facility, for any reason, may be more likely and able to participate.

Engaging digital intervention techniques are well-suited to health coaching as many of the effective strategies are common to both. While there is no single strategy that is effective for engagement for everyone, there are proven strategies to increase the likelihood of engagement and success. Specific strategies that the system will incorporate to increase engagement that work well with health coaching are goal setting, self-monitoring, interactivity, accountability and personalization. Goal Setting, which will be facilitated through health coaching, is most effective when it is used together with self-monitoring and accountability which increases engagement through enhanced motivation. Self-monitoring involves participants monitoring their own behavior in regard to a goal. In the proposed system, self-monitoring will be supported by providing data and feedback to the participants. Accountability will be facilitated by providing participant data to the health coaches who can help clarify the participant's goals, monitor progress, and reflect on their progress. The system will be interactive through the use of the health coaches, which has been found to be more engaging and more persuasive for digital health interventions. Finally, the system will support personalization and will be adaptive to individual's needs with the goal of behavior change. Other strategies may be incorporated as they are deemed effective in development and testing (e.g., reminders). The proposed system will be built for usability and with high quality visual design. While usability itself does not increase engagement, a system that is not usable will be a barrier to the program and technology use. A high quality visual design supports usability and it can directly impact engagement. We propose a user-centered design process to ensure the usability and appeal of the visual design of the system.

Preliminary evidence shows that an effective digital health intervention that utilizes remote monitoring and health coaching to address obesity may be as effective as an in-person program, in addition to having benefits in accessibility and scalability. Recent preliminary research also shows that this type of intervention is feasible, acceptable, and effective for older adults living in rural areas to address obesity. This is particularly important as there has been limited study of older adults participation in digital health interventions.

**Scientific Premise :** Severe OSA associated with obesity and other comorbidities is highly influenced by behavior. Early evidence suggests that health coaching is effective at supporting patients with behavior changes and chronic disease management. Health coaching associated with remote monitoring has been tested and offers promise to address behavior, including PAP use, physical activity, and mindful eating. Based on our previous NIH funded work in other chronic conditions, we hypothesize that a remote monitoring system with health coaching for severe OSA with obesity and comorbidity is feasible and may improve quality of life. Additionally, it may create conditions for behavior change resulting in increased adherence to PAP use as well as addressing obesity and other comorbid conditions. If effective these findings are extremely important to

addressing a critical health problem through a solution that is relatively inexpensive, scalable, billable, and accessible.

We propose to develop a home-based system for obese patients with OSA. The proposed system will provide patients with remote guidance, personalized reports, and monitoring integrated with health coaching. Health coaches will also receive individualized patient information, formatted in accessible and usable way.

Monitoring will include key indicators: PAP use, sleep quality, physical activity, weight and symptom days (self-reported well-being, fatigue, sleepiness, and daily activity). The system is compliant to bill for remote patient monitoring through existing Medicare and private insurance billing codes.

## Study Design and Methods

**Methods:** *Describe in lay terms, completely detailing the research activities that will be conducted by Mayo Clinic staff under this protocol.*

The proposed system (see Figure 1) will use technology to facilitate remote health coaching for people with severe comorbid OSA with the goal of encouraging behavior change. The system will be built upon the existing home-based pulmonary rehabilitation (PR) system that was jointly developed by Mayo and MHS. The PR system was well-received and has proven effective, reliable, and easy to use. The overall architecture will be reused for the OSA coaching system, but a new set of sensors, cloud services, and data reporting capabilities will need to be integrated and developed.

The system will be designed so that a newly-diagnosed patient can immediately benefit from health coaching, including equipment setup, goal setting, and trend monitoring in all pertinent aspects of care: PAP management, sleep scheduling, sleep duration, diet, exercise, medications and more. When they register for the program, patients will be provided with a set of pre-configured sensors and a dedicated Android tablet. The tablet will exclusively run a custom-built Android application that graphs patient progress, asks periodic self-report questions, sends secure text messages between the health coach and patient, displays timely reminders, and plays helpful videos to assist with sensor use. The tablet and sensors upload the patient's activities, physiological data, and answers to the daily self-report questions to a secure website. This website also allows health coaches to view patient data via overview, weekly, daily, and trend reports. Health coaches call patients regularly to celebrate progress, assist with any issues, and set new goals.

**Figure 1.** A diagram of the proposed health coaching system.

In the past, MHS and Mayo jointly developed an in-home PR system that was well-received and is being widely deployed. Patients receive an Android tablet running an app that plays exercise videos, graphs patient progress, asks periodic self-report questions, sends text messages between the health coach and patient, displays timely reminders, and shows instructional videos to assist with sensor use. The app runs in “kiosk” mode, ensuring that the patient cannot close the app, accidentally misconfigure the tablet, or use the tablet for other purposes (e.g., web browsing, watching movies). Each tablet has a unique API key that allows it to sync the patient’s activities, physiological data, and daily self-report answers to a secure website. Health coaches can login to this website to review the data for each of their patients.

MHS engineers will provision a web server and database for the OSA coaching system. The web server will be an AWS EC2 t2.micro instance running Ubuntu Linux 18.04 with an .NET Core 3.1 application (or newer). The database will be an AWS RDS db.t2.micro instance running MariaDB 10.3.23 (or newer).

Software development best practices will be used throughout development. All source code will be versioned using Git and backed up GitHub.com.

Patients will be provided with a system (Android tablet linked to a Withings Body Smart scale, Withings Sleep Tracking Mat, and a Withings Move Activity and Sleep Watch, see Appendix 1 for Withings device information) to take home and instructions to use it for two weeks along with their newly prescribed PAP machine. Patients will be asked to weigh themselves at least once a week, to use the PAP machine and sleep mat daily, and to monitor their steps. Patients will also be asked to complete self-report questions at least 6 of the seven days and to complete a health coaching call twice per week. The activity monitor watch is to be worn

at all times. The participant tablet home screen display will have a simple To-Do list. To initiate an activity, the user selects the corresponding activity from the “To-Do” column. When the participant finishes the selected activity, it appears in the “Done” column. The application provides instructions before and between each activity. Participants will also be able to see limited reports of their activity as will the health coach. In phase II, this reporting capability will be flushed out. The health coaches are an established part of [name] laboratory and have been trained to support participants in the behavior change process.

The 5 self-reported questions are:

Tap the faces that best answer the following questions.					
How do you feel today?					
	POOR	FAIR	GOOD	VERY GOOD	EXCELLENT
How is your level of energy?					
	POOR	FAIR	GOOD	VERY GOOD	EXCELLENT
How was your sleep last night?					
	POOR	FAIR	GOOD	VERY GOOD	EXCELLENT
How was your CPAP experience last night? Leave blank if not used.					
	POOR	FAIR	GOOD	VERY GOOD	EXCELLENT
How was your awareness of what you ate yesterday?					
	POOR	FAIR	GOOD	VERY GOOD	EXCELLENT
CANCEL					

Following the 2 week testing period, participants will be interviewed by the Research Coordinator to provide qualitative feedback on the acceptability and usability of the system, including what they liked and did not like about the app interface, the concept of home-based system, and the health coaching. Participants will be asked to describe any struggles with using the system or past efforts in behavior change. Participants will also complete a brief socio-demographic survey. Additionally, the system securely collects and stores the following patient data: timestamped interactions with the Android app, answers to the daily questionnaire, physiological and activity data collected by the scale, sleep mat and activity monitor. All data will be reviewed and visualized to understand patient usage, identify potential barriers, and to plan further developments to the system.

The interviews will be recorded for subsequent transcription of the interactions. The transcribed interviews will be examined for common themes. Each interview will vary between 20 and 30 minutes and will be performed by a member of the Mindful Breathing Laboratory who is trained in Motivational Interviewing and Qualitative Interviewing. Additional members from the Lab will assist in the transcription of the interviews as well as theme identification. Data collection and analysis will be overseen by [name]. (A guided interview script will be used.)

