## Appendix 1:

### Withings Sleep Mat

#### Device

- **Outer material** Premium fabric
- **Dimensions and weight**
  - Length: 637mm (25")
  - Width: 190mm (7.5")
  - Thickness: 5mm (0.2")
  - Weight: 350 g (1.13 oz)
- **Sensors**
  - Pneumatic sensor: measures respiratory rate, heart beats via ballistocardiography and body movements across the mattress.
  - Sound sensor: identifies audio signals specific to snoring & cessation of breathing episodes.
- **Data storage & sync**
  - Free and unlimited online data storage with a Withings account.
  - Local storage of data between syncs.
- **Power supply**
  - Power supply 5V 1A
  - USB power adapter included

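### PAP use is the first-named key indicator, but the only structured PAP item shown is left blank for non-use, so the questionnaire alone cannot tell a night without PAP from a skipped item

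*Protocol*

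**What the plan says.** The Scientific Premise part of the protocol's Research Question and Aims states: "Monitoring will include key indicators: PAP use, sleep quality, physical activity, weight and symptom days". Study Design and Methods says the system is designed to support "trend monitoring in all pertinent aspects of care: PAP management, sleep scheduling, sleep duration, diet, exercise, medications and more".

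For the two-week home test, the same section says: "Patients will be asked to weigh themselves at least once a week, to use the PAP machine and sleep mat daily". The tablet is linked to a scale, a sleep mat and an activity watch. The stored data are "timestamped interactions with the Android app, answers to the daily questionnaire, physiological and activity data collected by the scale, sleep mat and activity monitor". Neither list names a record from the PAP machine.

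The fourth of the five daily questions is "How was your CPAP experience last night? Leave blank if not used". It is answered on a five-point scale from poor to excellent. The options include no response for non-use, and no separate item asks whether or for how long PAP was used.

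The stated purpose of the data is: "All data will be reviewed and visualized to understand patient usage, identify potential barriers", and to plan further development of the system.

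**The concern.** The instruction makes a blank the code for non-use. A blank is also what remains when a participant passes over the item. Once a form is submitted, the two look alike in the questionnaire data.

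This matters because a night without PAP is just the kind of usage signal and barrier that the data review is meant to find, and non-use is not expected to be rare. The protocol's own background says that acceptable adherence at 31 to 90 days is seen in only 75% of patients, and recruitment is tied to a visit 2 or 3 months after the initial consultation.

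This is a rule about how data are captured. If two states are stored identically, a later analysis rule can only assume which one occurred.

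**Working it through.** The protocol gives no figure to reproduce here, so the check has two parts: which stored data could resolve a blank, and how large the ambiguity could be.

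**Could another listed source resolve a blank?**

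- *App timestamps.* These can separate a form never opened from one submitted. An item left untouched would be expected to leave no tap, whether PAP was unused or the item was skipped. This is an inference, because the protocol does not describe the log in detail.
- *Sleep mat.* Appendix 1 says: "Sound sensor: identifies audio signals specific to snoring & cessation of breathing episodes". That is indirect evidence about the night, not a record of PAP use.
- *Coaching calls, requested twice a week.* A coach could ask about a blank, but no structured night-by-night PAP record from the calls is described.
- *Exit interview.* "Participants will be asked to describe any struggles with using the system or past efforts in behavior change". This may bring out non-use in general terms, but it does not reconstruct individual nights.
- *Medical record.* The section Review of medical records, images, specimens gives eligibility and contact information as the purpose, not PAP usage.

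**How large is the ambiguity?**

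Inputs:

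- Submitted forms per participant: 12. The protocol asks for at least 6 of 7 days over two weeks, and 6 × 2 = 12. That every participant submits exactly this number is an assumption.
- Rated nights, *r*: 8 or 10 (assumed).
- Skip rate on PAP nights, *s*: 5%, 10% or 20% (assumed; the protocol gives none).

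Formulas:

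- Nights used = *r* / (1 − *s*)
- Nights skipped = *r* × *s* / (1 − *s*)
- Blanks = 12 − *r*
- Share of blanks misread as non-use = nights skipped / blanks

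| *r* | Blanks | *s* | Nights used | Use on form nights | Nights skipped | Blanks misread |
|---|---|---|---|---|---|---|
| 8 | 4 | 0 | 8.00 | 66.7% | 0 | 0 |
| 8 | 4 | 5% | 8.42 | 70.2% | 0.42 | 10.5% |
| 8 | 4 | 10% | 8.89 | 74.1% | 0.89 | 22.2% |
| 8 | 4 | 20% | 10.00 | 83.3% | 2.00 | 50.0% |
| 10 | 2 | 0 | 10.00 | 83.3% | 0 | 0 |
| 10 | 2 | 5% | 10.53 | 87.7% | 0.53 | 26.3% |
| 10 | 2 | 10% | 11.11 | 92.6% | 1.11 | 55.6% |

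With 10 rated nights, a 20% skip rate is impossible, since 10 / 0.8 = 12.5 exceeds 12. The largest possible rate is 2/12 = 16.7%.

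**A bound that needs no skip rate.** If a share *b* of submitted forms has a blank PAP item, use on those nights lies anywhere from 1 − *b* to 100%. With 8 rated nights, *b* = 4/12 and the range is 67% to 100%. With 10, *b* = 2/12 and the range is 83% to 100%. The questionnaire alone cannot narrow either range.

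**The case against.** The strongest reply is that the item asks about experience and does not claim to measure use. The Scientific Premise lists PAP use separately from the symptom items, and only the latter are labelled self-reported. For an experience rating, leaving the item blank when it does not apply is a reasonable instruction. The blank matters for PAP use only if no other source exists, and that cannot be confirmed. Figure 1, the system diagram, is not shown, and Study Design and Methods says new sensors and cloud services are still to be integrated. This stands as a limit on confidence. The written device and data lists nevertheless name no PAP record.

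A second reply is that storage behaviour is inferred, because the app might prompt for omissions. That is possible, but no prompt is described. Since a blank is the instructed answer for non-use, the app must accept one on this item.

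Third, coaches can view daily reports and are due to call twice a week, and barriers in a 15-person qualitative study are likely to come up in conversation. This will help for some nights, but it does not separate the two states in the stored data.

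Finally, no adherence endpoint is stated, the protocol plans a qualitative analysis, and the skip rates above are hypothetical. All of this is correct. At a 5% skip rate the shift is about half a night per participant, and the larger shares of misread blanks rest on only four or two blanks. This keeps the point small but does not remove it.

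**Conclusion.** The concern holds, as a minor one. In the visible text, the only structured PAP item stores non-use and a skipped item in the same way, and no listed data source separates them night by night.

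On the assumed 12 forms, the shift in nights used is about half a night at a 5% skip rate (0.42 or 0.53), about one night at 10% (0.89 or 1.11), and two nights at 20% with 8 rated nights. At a given skip rate, the share of blanks misread is larger for the more regular user: 56% against 22% at 10%.

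No planned conclusion fails. The loss is limited to interpretable PAP-use data for the usage and barrier review and for further development of the system. Confidence is medium, because a PAP feed in Figure 1 cannot be excluded.

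**What to change.** Replace the leave-blank instruction with an explicit response such as *Did not use PAP last night*, so that a blank means missing only. The item can stay optional. For each participant, report nights used, not used and missing, and show the experience rating beside the count of non-use nights.

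If PAP-machine usage data are already available to the team, name them as the source for the PAP-use indicator. If they come through the medical record, widen the purpose stated under Review of medical records, images, specimens, which now covers only eligibility and contact information.

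The cost is one response option in an app still being developed and at most one extra tap a day for the participant. Some participants may be reluctant to report non-use openly. If the team chose to make the item compulsory, there would also be some risk of careless answers. Naming a machine record, where one exists, adds about one sentence.
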